12.2.8. Treatment of Overdose of Investigational Drug

An overdose is any dose of investigational drug given to a patient or taken by a patient that exceeds the dose described in the protocol. There is no information regarding overdose with RPC1063. Any overdose, with or without associated AEs, must be promptly reported to the CRO's Medical Monitor or other designated Drug Safety Center. Overdoses do not need to be recorded as AEs in the eCRF; only in the case of any AEs associated with the overdose should these be reported on relevant AE/SAE sections in the eCRF.

12.2.9. Procedures in Case of Pregnancy

If a urine pregnancy test is positive, the patient will be instructed to suspend further study dosing. If the test was performed by the patient between scheduled visits, a follow-up appointment will be scheduled as soon as possible. A serum pregnancy test will be performed to confirm the result.

Pregnancy in itself is not regarded as an AE unless there is a suspicion that an investigational product may have interfered with the effectiveness of a contraceptive medication; however, the outcome of all pregnancies (spontaneous miscarriage, elective termination, normal birth,

or congenital abnormality) must be followed up and documented even if the patient was discontinued from the trial. In cases of live birth, the infant will be followed for up to a year.

Male patients should also be instructed to notify the Investigator in the event that their female partner becomes pregnant. Attempts should be made to follow female partners of trial patients, if they should become pregnant. The Investigator must obtain informed consent/assent from the pregnant partner of a trial patient prior to collecting data on her pregnancy and its outcome.

All reports of congenital abnormalities/birth defects are SAEs. Spontaneous miscarriages should also be reported and handled as SAEs. Elective abortions without complications should not be handled as AEs. All outcomes of pregnancy must be reported to the Sponsor and/or its designee. In cases of live birth, the infant will be followed for up to a year.

12.2.10. Data Safety Monitoring Board

An independent DSMB will be charged with monitoring accumulating safety data from the trial, as well as general aspects of trial conduct.

The committee will meet periodically during the trial (approximately 4 times each year) to review aggregate analyses by treatment group concerning enrollment, treatment compliance, adherence to follow-up schedule, and safety data from the trial. The DSMB may recommend modifying or stopping the trial early due to safety concerns based on data reviews.

The blinding plan to assure that all personnel involved in the conduct of the trial remain blinded to the results of interim reviews will be specified in the DSMB Charter.

[REDACTED]

[REDACTED]

[REDACTED]

- [REDACTED]
- [REDACTED]
- [REDACTED]

[REDACTED]

[REDACTED]

- [REDACTED]

12.4. Appropriateness of Measurements

The efficacy and safety assessments are standard assessments and deemed to be reliable, accurate, and relevant for this indication and patient population.

13. PLANNED STATISTICAL METHODS

13.1. Determination of Sample Size

Induction Period:

Cohort 1 (adult patients): Based on results from a previous Phase 2 induction trial of RPC1063 1 mg, it is anticipated that at least 16% of patients in the RPC1063 group and approximately 6% of patients in the placebo group will be in clinical remission at the end of the IP. Based on a 2-sided Fisher's exact test at $\alpha = 0.05$, a sample size of approximately 600 patients randomized in a 2:1 ratio in Cohort 1 (400 RPC1063 1 mg and 200 placebo) will provide at least 90% power to detect this difference of 10 percentage points.

Cohort 2 (adult patients): Based on the same Phase 2 trial, it is anticipated that at least 60% of patients treated with RPC1063 will have a clinical response at the end of the IP. In order to ensure that there are approximately 420 patients with a clinical response to RPC1063 for potential enrollment of approximately 400 patients into the MP (assuming a 5% dropout rate), it will be necessary to enroll approximately 900 adult patients overall into the IP, of which 700 will receive treatment with RPC1063. Therefore, approximately an additional 300 patients receiving RPC1063 1 mg will be enrolled into Cohort 2.

Table 5: Sample Size and Corresponding Precision

Total Sample Size	Sample Size by Treatment		Precision: Half-Width of a 95% Confidence Interval for Treatment Difference (Ozanimod Versus Placebo)	
	Ozanimod	Placebo	Clinical Remission $\Delta=10\%$ (16% versus 6%)	Clinical Response $\Delta=25\%$ (57% versus 32%)
30	20	10	21.8%	36.1%
60	40	20	15.4%	25.6%
90	60	30	12.6%	20.9%
120	80	40	10.9%	18.1%
150	100	50	9.7%	16.2%

Maintenance Period (adult patients):

The placebo remission rate at Week 42 (52 weeks total treatment) is assumed to be 16% in a randomized withdrawal trial in UC patients who have previously had a clinical response to induction therapy (Feagan et al, 2013). Based on a 2-sided Fisher’s exact test at alpha = 0.05, a sample size of 400 patients (200 patients per treatment group) will provide 90% power to detect a statistically significant improvement in the remission rate of 14 percentage points or larger (ie, an active group remission rate of 30% or higher). To account for a 5% rate of patients who had a clinical response to induction therapy with RPC1063 not entering the MP, approximately 420 patients with a clinical response to RPC1063 will be required at the end of the IP.

The placebo remission rate at Week 42 (52 weeks total treatment) in the subset of patients who are in remission at Week 10 is assumed to be 16% (remission-in-remitters). Based on a 2-sided Fisher’s exact test at alpha = 0.05, a sample size of 120 patients (60 per treatment group) will provide approximately 80% power to detect a statistically significant improvement in the remission-in-remitters rate of 24 percentage points or larger (ie, an active group remission-in-remitter rate of 40% or higher). As Cohort 2 is open-label, the ongoing remission rate at Week 10 from this cohort will be tracked and if it becomes evident that there will be fewer than 66 remitters from Cohort 2 entering MP, the sample size of Cohort 2 will be increased in proportion to the number of remaining remitters necessary to achieve approximately 66, which may in turn increase the number of patients from Cohort 2 qualifying to enter MP. To ensure adequate powering for the MP and a total of approximately 110 remitters, it may be necessary to increase the number of patients in Cohort 2 and therefore the total number of patients in the study.

13.2. Statistical Methods

13.2.1. General Considerations

For the purposes of statistical analyses, the IP and the MP will be treated as two independent trials. The analysis of the IP will formally evaluate the efficacy and safety of RPC1063 1 mg vs. placebo as an induction therapy and the analysis of the MP will formally evaluate the efficacy and safety of RPC1063 1 mg vs. placebo as a maintenance therapy.

All efficacy and safety data will be listed by patient. Baseline for the IP is defined as the last observed measurement prior to the Day 1 receipt of investigational drug. Baseline for the MP is defined as the last observed measurement prior to the first dose of investigational drug following randomization into the MP. All safety and efficacy endpoints will be summarized by treatment group.

In general, descriptive summaries will be presented for the efficacy and safety variables collected. Continuous variables will be summarized using number of patients (n), mean, standard deviation (SD), minimum, median, and maximum. Categorical variables will be summarized using frequency counts and percentages.

13.2.2. Analysis Populations

All patient populations will be defined and documented prior to database lock. The following analysis populations will be used in the statistical analysis:

- Intent-to-Treat (ITT) population: The ITT population will consist of:
 - **Induction Period Cohort 1:** All randomized adult patients from Cohort 1 of the IP of the trial who received at least 1 dose of investigational drug (RPC1063 or placebo)
 - **Induction Period Cohort 2:** All enrolled adult patients from Cohort 2 of the IP of the trial who received at least 1 dose of investigational drug (RPC1063)
 - **Maintenance Period:** All randomized patients who received at least 1 dose of investigational drug (RPC1063 or placebo) in the MP

The ITT populations will be used as the primary population for all efficacy parameters. Patients who prematurely withdraw from the trial for any reason and for whom an assessment is not performed for any reason will still be included in the ITT analyses. Patients who receive an incorrect investigational drug from that which was randomized will be summarized in the treatment group according to the intended randomization.

- Per Protocol (PP) population: The PP population will consist of all patients in the ITT populations who adhere to the protocol. This population will be used in sensitivity analyses of the primary and key secondary endpoints to evaluate the influence of major protocol violators and protocol deviators on the primary

results. Patients may be excluded from this population if they violate the eligibility criteria or significantly deviate from the trial plan. Specific reasons for warranting exclusion from this population will be documented prior to database lock and may include, but are not limited to, investigational drug noncompliance > 20%, receiving incorrect investigational drug for more than 1 week in the IP or more than 1 month in the MP, and missing more than 2 visits while still on the trial.

- Safety population: The Safety population will consist of all patients who receive at least 1 dose of investigational drug. This population will be used for all summaries of safety data. Patients randomized to placebo who receive any amount of RPC1063 will be summarized in the RPC1063 1 mg group. Patients randomized to RPC1063 who receive only placebo for all doses will be summarized in the placebo group, otherwise they will be summarized in the RPC1063 1 mg group.

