Note: Adult patients in Cohort 1 will be randomized to receive RPC1063 or placebo in a 2:1 ratio in a double-blinded manner. Adult patients in Cohort 2 will receive RPC1063 in an open-label manner. Adult patients in clinical response at Week 10 of the IP who were randomized to placebo (Cohort 1) will continue to receive placebo in the MP in a double-blind manner. Only responders assigned to RPC1063 (Cohort 1 and 2) in the IP will be randomized to receive RPC1063 or placebo in a 1:1 ratio in a double-blinded manner when entering the MP.

[figure not shown]

Table 1: Schedule of Events

Trial Procedures	Screening	Induction			Maintenance							Early Term ^g	Safety Follow-up ^h	
		Dose Escalation	Assigned Dose		Treatment									
(Visit Label)	Day -35 to 0	Visit I 1 ^{a,b} (Week 0)	Visit I 2 ^a (Week 5)	(EoT) Visit I 3 ^b (Week 10)	Visit M 1 ^{b,c} (Week 0)	Visit M 2 (Week 8)	Visit M 3 (Week 18)	Visit M 4 (Week 30)	Relapse Visit (When Indicated)	(EoT) Visit M 5 ^b (Week 42)	Day 294±10	Day of Early Term	Last dose + 30 to 60 days	Last dose + 90 days ± 10 days ⁱ
(Overall Duration)	Day -35 to 0	0 weeks	5 weeks	10 weeks	10 weeks	18 weeks	28 weeks	40 weeks		52 weeks				
Informed consent/assent	X													
Inclusion/exclusion criteria	X	X			X									
Demographics	X													
Medical history ^{d,e}	X	X												
Viral serology ^f	X													
Stool culture ^g	X													
Randomization		X			X									
Dispense investigational drug		X	X	X ^b	X	X	X	X	X	X				
Administer investigational drug at clinic		X		X	X						X			
Review drug compliance			X	X	X	X	X	X	X	X	X	X		
Prior and concomitant medications	X	X	X	X	X	X	X	X	X	X	X	X	X	X
Medical procedures (non-trial)		X	X	X	X	X	X	X		X	X	X		

	Trial Procedures	Screening	Induction			Maintenance						Early Term ⁹	Safety Follow-up ⁸		
			Dose Escalation	Assigned Dose		Treatment									
(Visit Label)	(Visit Day and Window)	Day -35 to 0	Visit I 1 ^{a,b} (Week 0)	Visit I 2 ^w (Week 5)	(EoT) Visit I 3 ^b (Week 10)	Visit M 1 ^{b,c} (Week 0)	Visit M 2 (Week 8)	Visit M 3 (Week 18)	Visit M 4 (Week 30)	Relapse Visit (When Indicated)	(EoT) Visit M 5 ^b (Week 42)	Day of Early Term	Last dose + 30 to 60 days	Last dose + 90 days ± 10 days ^t	
(Overall Duration)			0 weeks	5 weeks	10 weeks	10 weeks	18 weeks	28 weeks	40 weeks		52 weeks				
Safety Assessments	Adverse events ^z		X	X	X	X	X	X	X	X	X	X	X	X	
	12-Lead ECG	X	X		X						X	X		X ^y	
	Vital signs	X	X	X	X	X	X	X	X		X	X	X	X ^y	
	Hematology ^v	X	X	X	X	X	X	X	X		X	X	X	X	

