13.4.2. Maintenance Period (Adult Patients)

Patients with a clinical response [REDACTED] at Week 10 will be eligible to enter the MP. Patients who received RPC1063 1 mg and showed a clinical response during the IP (both Cohort 1 and Cohort 2) will be randomized in a double-blind manner to receive either RPC1063 1 mg or placebo in a 1:1 ratio. Patients randomized to placebo in Cohort 1 who demonstrate a clinical response during the IP will continue to receive placebo in the MP. Patients from either Cohort who do not show a clinical response may enter an optional Open-Label Extension trial, if appropriate.

MP endpoints are listed in [Section 6.2.4](#).

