13.4.3. Safety Analyses

All safety analyses will be carried out on the Safety population.

Adverse events will be monitored during the trial and the data analyzed with respect to incidence within each treatment group as well as severity and potential relationship of the AEs to investigational drug. Adverse events with onset on, or after the first dose of investigational drug or with onset prior to the first dose of investigational drug that increase in severity on, or after the first dose of investigational drug will be considered treatment-emergent. Treatment-emergent AEs will be summarized for the Safety population by System Organ Class and Preferred Term, and presented in descending order of frequency within each System Organ Class. Serious AEs and AEs leading to discontinuation will be summarized similarly.

Associated laboratory parameters such as hepatic profile, renal function, and hematology values will be grouped and presented together. For each laboratory test, individual patient values outside the standard reference range will be flagged and listed. Shift tables will be produced showing the frequency of shifts from Baseline to the lowest and to the highest on-trial value in and out of the normal range as well as by visit. Changes from Baseline to each visit for each laboratory parameter will also be summarized.

The change from Baseline to each visit for each of the vital sign variables will be summarized. Abnormal vital sign values will be flagged and listed.

The change from Baseline to each visit for each of the ECG parameters will be summarized. An outlier analysis of ECG results will be conducted.

The change from Baseline for each of the PFT parameters will be summarized. An outlier analysis of PFT results will be conducted.

OCT parameters will be summarized.

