11.1. Adverse Events

AEs will be monitored during the trial and the data analyzed with respect to incidence within each treatment group as well as severity and potential relationship of the AEs to investigational drug.

A serious adverse event (SAE) is any untoward medical occurrence that at any dose results in death, is life-threatening, requires inpatient hospitalization or prolongation of existing inpatient hospitalization, results in persistent or significant disability/incapacity, is a congenital abnormality/birth defector is an important medical event that may not be immediately life-threatening or result in death or hospitalization but jeopardize the patient or may require intervention to prevent one of the other outcomes listed in the definition above.

A treatment-emergent adverse event (TEAE) is any AE that emerges during treatment having been absent pre-treatment, or worsens relative to the pre-treatment state, excluding those with onset after first MP dose.

An overall summary of TEAEs during IP will include the number and percentage of patients with

- ≥ 1 TEAE
- ≥ 1 Moderate or Severe TEAE
- ≥ 1 Severe TEAE
- ≥ 1 Possible, Probable or Related TEAE
- ≥ 1 Related TEAE
- ≥ 1 Serious TEAE
- ≥ 1 Possible, Probable or Related Serious TEAE
- ≥ 1 Related Serious TEAE

- ≥ 1 TEAE Leading to Discontinuation of Study Drug
- ≥ 1 TEAE Leading to Interruption of Study Drug
- Death
- Death Related to Study Drug

TEAEs will also be summarized and presented by decreasing frequency in the sort keys below in the Cohort 1 RPC1063 1 mg group:

- by system organ class and preferred term: all TEAEs, related TEAEs, severe TEAEs, serious TEAEs, possible, probable or related serious TEAEs, TEAEs leading to interruption of study drug, TEAEs leading to discontinuation of study drug
- by preferred term: all TEAEs, TEAEs with $\geq 2\%$ higher incidence rate in RPC 1 mg than placebo, TEAEs with incidence rate $\geq 5\%$, TEAEs with incidence rate $\geq 2\%$
- by system organ class, preferred term, and maximum severity: all TEAEs

Patients with multiple events reported for the same summary level will be counted only once.

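### Does the Safety population rule move patients re-randomized to placebo into the RPC1063 column in the Maintenance Period?

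*Protocol*

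**What the plan says.** Protocol 13.2.2 defines the ITT population by period. Its MP part reads "All randomized patients who received at least 1 dose of investigational drug (RPC1063 or placebo) in the MP". The Safety population in the same section requires only one dose of investigational drug and names no period. Its as-treated rule is "Patients randomized to placebo who receive any amount of RPC1063 will be summarized in the RPC1063 1 mg group". The companion sentence keeps patients randomized to RPC1063 in the RPC1063 group unless every dose they took was placebo.

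Protocol 13.4.3 defines treatment-emergent events, in part, as "Adverse events with onset on, or after the first dose of investigational drug", again without a period.

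The design has two kinds of MP placebo patient. The note to Figure 1 in Protocol 7.1 says "Only responders assigned to RPC1063 (Cohort 1 and 2) in the IP will be randomized to receive RPC1063 or placebo in a 1:1 ratio". Protocol 13.4.2 adds "Patients randomized to placebo in Cohort 1 who demonstrate a clinical response during the IP will continue to receive placebo in the MP".

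Protocol 13.2.1 sets the frame: "For the purposes of statistical analyses, the IP and the MP will be treated as two independent trials". It then says that the MP analysis evaluates efficacy and safety against placebo, and fixes a new starting point: "Baseline for the MP is defined as the last observed measurement prior to the first dose of investigational drug following randomization into the MP".

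The supplied SAP covers only adult IP data, and its Introduction leaves the MP to a separate SAP. Its section 5.3 repeats the as-treated sentence unchanged. Its section 11.1 limits IP treatment-emergent events by "excluding those with onset after first MP dose".

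**The concern.** The contrast within 13.2.2 draws the eye: the ITT definition was split by period and the Safety definition was not. In a randomized-withdrawal design that omission could matter, because every patient re-randomized to placebo has already taken RPC1063. Taken word for word, the as-treated rule would empty the randomized placebo arm into the RPC1063 column. The only placebo patients left would be Cohort 1 placebo responders, who were never re-randomized.

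A second question survives even if the rule is read within the period. Safety membership needs a dose, not MP randomization, so a single placebo column could mix withdrawn patients with never-exposed ones. Appendix 3 of the protocol reports a median of 30 days for lymphocytes to return to normal after stopping 0.92 mg, with about 90% of subjects recovered within 90 days. The two groups would therefore differ in residual drug effect early in the MP. Likewise, a treatment-emergent rule with no MP start could carry IP events into MP tables.

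**Working it through.** **The plan's own figures.** Protocol 13.1 plans 200 per group in the MP for 90% power at 30% versus 16%, two-sided Fisher test, alpha 0.05. Exact enumeration gives 90.0%, so the figure reproduces. The supply of responders also agrees: 700 × 0.60 = 420, and 420 × 0.95 = 399, against a target of about 400. None of this depends on the Safety definition.

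**Inputs for the column counts.** The MP has 200 + 200 re-randomized patients (Protocol 13.1) and the IP has 200 placebo patients (Cohort 1). The documents give no adult planning rate for placebo response. I assume 32%, borrowed from Table 5 (a precision table for totals of 30 to 150), and show 20% to 50%. I also assume that all placebo responders enter the MP.

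Continuing-placebo patients = 200 × response rate:
- 20%: 200 × 0.20 = 40
- 32%: 200 × 0.32 = 64
- 50%: 200 × 0.50 = 100

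**Reading A: as-treated rule applied across the whole trial.** RPC1063 column = 200 + 200 = 400, of whom 200/400 = 50% were assigned to placebo. Placebo column = about 64 (40 to 100), none of them re-randomized.

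**Reading B: rule applied within the MP, one placebo column.** RPC1063 = 200. Placebo = 200 + 64 = 264. Share never re-randomized:
- 20%: 40/240 = 17%
- 32%: 64/264 = 24%
- 50%: 100/300 = 33%

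**Reading C: within the MP, continuing-placebo patients shown apart.** 200 versus 200, plus a separate group of about 64.

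**Which reading the text supports.**

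1. Section 13.2.1 treats the periods as independent trials and names safety expressly. In the MP trial, assignment and receipt then mean assignment and receipt in the MP. Reading A leaves no randomized placebo patient for the MP safety comparison that the same section promises, so it defeats the section's stated purpose.
2. The as-treated rule is a provision for patients given the wrong drug, written for one assignment per patient. Under Reading A a re-randomized Cohort 1 patient carries two assignments.
3. SAP 5.3 uses the identical sentence, with no period words, in a document confined to IP data. There it works as a single-period rule, so the missing words do not signal pooling across periods.
4. SAP 11.1 ends IP treatment-emergent events at the first MP dose. With the MP as its own trial and its Baseline set just before its first dose, the natural start for MP events is that same dose.

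**Reading B or C.** The protocol does not settle table columns. It does not separate Cohort 1 from Cohort 2 for safety either, yet SAP section 11 presents safety by treatment and cohort. The level of detail in question is the kind that the period SAP supplies. Protocol 9.8 already refers to the randomized component of the MP, so the distinction between the two placebo groups is recognized.

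**The case for a change.** The best case for a change is that 13.2.1 states a principle but gives no as-treated rule, so strictly nothing overrides the sentence in 13.2.2. The authors wrote period limits into the ITT definition and into the Per Protocol examples in the same section, so they knew how to do it. The within-period reading still leaves the continuing-placebo patients unplaced. Even the MP Baseline is tied to an MP randomization that they do not undergo. The IP SAP copied the Safety wording unchanged, and the MP SAP might do the same. Adding the words would cost almost nothing.

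The factual part of this stands: the period words are absent, and no supplied text assigns a column or an explicit MP Baseline to these patients. The inference to a faulty analysis does not stand. It needs analysts to read one sentence against the section that frames it, or to merge two groups that the design keeps distinct. Nor does a copied sentence prove a defect, since in the MP SAP it would again operate within one period. The residual lymphocyte effect is also no argument against the randomized comparison: it is present in the withdrawn arm however the columns are drawn, and it concerns the early part of 42 weeks.

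**Conclusion.** This is missing detail that analysts would fill sensibly, and no change to the plan follows. The wholesale reclassification arises only if 13.2.2 is read apart from 13.2.1. On the within-period reading, all 200 planned patients re-randomized to placebo stay in the placebo group.

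The open item is whether continuing-placebo patients share that column. If they did, they would be about 24% of it (17% to 33%). That range rests on an assumed placebo response and on all responders entering the MP. It describes the make-up of a column and is not a bias in a safety estimate. The safety analyses in 13.4.3 are descriptive summaries. MP efficacy is analysed on randomized patients, so the 90% power is untouched.

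The conclusion is limited by the MP SAP not being among the documents. Its absence here does not show that the rules are absent from it. Anyone who holds it can confirm that safety assignment and treatment-emergent events run from the first MP dose, and that continuing-placebo patients are shown separately.
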